5.7.6. Infectious Events

Patients with lymphoid cancers receiving idelalisib have developed serious and fatal infections during therapy. Opportunistic infections, most notably *Pneumocystis jirovecii* pneumonia (PJP) and CMV infection, have most frequently occurred within the first 6 months of treatment with idelalisib and are increased in the context of concurrent myelosuppressive therapy such as bendamustine.

Subjects must receive prophylaxis for PJP throughout the course of idelalisib treatment, and for 2 to 6 months after idelalisib treatment ends (see Section 5.8.1). Subjects must permanently discontinue idelalisib upon diagnosis of PJP.

Cytomegalovirus (CMV) surveillance for active disease (quantitative PCR or PP65 antigen) must be conducted approximately every 4 weeks throughout the course of idelalisib treatment. CMV viral load testing should be performed from the same specimen type whenever possible and caution should be exercised when comparing CMV viral load results across different testing centers. If unequivocal clinical or laboratory evidence of CMV infection is present, the subject must interrupt idelalisib treatment and undergo effective antiviral treatment according to established clinical guidelines. If the benefits of resuming idelalisib are judged to outweigh the risks, consider pre-emptive CMV therapy.

In high-risk subjects (history of recurrent infection, allogeneic transplant, treatment with alemtuzumab, hypogammaglobulinemia) other infection prophylaxis should be considered per consensus guidelines. Administration of intravenous immunoglobulin is permitted per standard institutional practice {[Raananani 2009](#)}. For subjects who develop an infection, appropriate medical therapy should be instituted in a timely manner.

5.7.7. Secondary Malignancies

Subjects receiving idelalisib for CLL or iNHL have developed pre-malignant and secondary malignant diseases, such as basal cell carcinoma, myelodysplastic syndrome, myeloproliferative disorders, and more aggressive lymphoid malignancies (eg, have had Richter transformation). Generally this has occurred in subjects who have received multiple previous lines of therapy and when idelalisib is combined with other therapies such as rituximab or bendamustine. The specific association of the therapeutic agents with these types of events has not been determined.

5.7.8. Ultraviolet Exposure

In vitro studies indicate enhanced cytotoxicity when embryonic murine fibroblasts treated with GS-563117 (the major metabolite of idelalisib) are simultaneously exposed to ultraviolet light. While nonclinical findings suggest the hypothetical potential for phototoxicity in humans, available clinical data do not reveal a photosafety concern. Although specific clinical correlates for these nonclinical data are not available, investigators and study subjects should be observant for the possibility that study participants may have exaggerated sunburn reactions (eg, burning, erythema, exudation, vesicles, blistering, edema) involving areas of skin exposed to ultraviolet light.

5.7.9. Pregnancy, Lactation, and Reproduction

Idelalisib has induced embryo lethality and teratogenicity when administered to pregnant female rats at maternally toxic doses. However, definitive reproductive toxicology studies in animals have not yet been performed and the specific effects of idelalisib on human embryogenesis or fetal development are unknown. Whether idelalisib is excreted in human breast milk is unknown. General toxicology studies of idelalisib in rats and dogs indicated dose-dependent reductions in testicular weights, with persistent minimal to mild degeneration of the seminiferous tubules and decreased spermatozoa in rats and hypospermatogenesis in dogs. The implications of these testicular changes for animal or human fertility are unknown.

Given the potential the risks to a fetus or infant as a result of exposure to idelalisib, women of reproductive potential entering this study must have a negative serum pregnancy test at baseline and must not be breastfeeding. Males and females of childbearing potential should abstain from sexual intercourse or use an effective form of contraception (see [Appendix 5](#)). If a female study participant becomes pregnant or decides to breastfeed during the course of the study, all study therapy (idelalisib//BI836826) must be discontinued.

5.7.10. *Pneumocystis jirovecii* Pneumonia Prophylaxis

Trimethoprim sulfamethoxazole is rated a Pregnancy Category C agent. In rats, oral doses of 533 mg/kg or 200 mg/kg produced teratologic effects manifested mainly as cleft palates. One survey found no congenital abnormalities in 35 children whose mothers had received oral sulfamethoxazole and trimethoprim at the time of conception or shortly thereafter. Because sulfamethoxazole and trimethoprim may interfere with folic acid metabolism it should be used during pregnancy only if the potential benefit justifies the potential risk to the fetus.

Dapsone is rated a Pregnancy Category C agent. Extensive, but uncontrolled experience and 2 published surveys on the use of Dapsone in pregnant women have not shown that Dapsone increases the risk of fetal abnormalities if administered during all trimesters of pregnancy or can affect reproduction capacity. Because of the lack of animal studies or controlled human experience, Dapsone should be given to a pregnant woman only if clearly needed. Dapsone is excreted in breast milk in substantial amounts. Hemolytic reactions can occur in neonates. Because of the potential for tumorigenicity shown for Dapsone in animal studies a decision should be made whether to discontinue nursing or discontinue Dapsone, taking into account the importance of drug to the mother.

Atovaquone is rated a Pregnancy Category C agent. Atovaquone is teratogenic and did not cause reproductive toxicity in rats at plasma concentrations up to 2 to 3 times the estimated human exposure. Atovaquone can cause maternal toxicity in rabbits at plasma concentrations that were approximately one half the estimated human exposure. Mean fetal body lengths and weights were decreased and there were higher numbers of early resorption and post-implantation loss per dam. It is not clear whether these effects are caused by atovaquone directly or are secondary to maternal toxicity. Concentrations of atovaquone in rabbit fetuses averaged 30% of the concurrent maternal plasma concentrations. There are no adequate and well-controlled studies in pregnant women. Atovaquone should be used during pregnancy only if the potential benefit justifies the potential risk to the fetus. It is not known whether atovaquone is excreted into human milk. Because many drugs are excreted into human milk, caution should be exercised when Atovaquone is administered to a nursing woman. In a rat study, atovaquone concentrations in the milk were 30% of the concurrent atovaquone concentrations in the maternal plasma.

Aerosolized Pentamidine (NebuPent) is a Pregnancy Category C agent. There are no adequate and well controlled studies of NebuPent in pregnant women. One literature report indicated that intravenously administered pentamidine in pregnant rats at 4 mg/kg/day was embryolethal; however, teratogenicity was not observed in this study. It is unknown whether pentamidine administered via the aerosolized route crosses the placenta at clinically significant concentrations. It is not known whether NebuPent can cause fetal harm when administered to a pregnant woman. NebuPent should be given to a pregnant woman only if clearly needed. It is not known whether NebuPent is excreted in human milk. NebuPent should not be given to a nursing mother unless the potential benefits are judged to outweigh the unknown risks.

5.7.11. Risk of Hepatitis B Reactivation

Hepatitis B Virus (HBV) reactivation can occur in patients treated with anti-CD20 antibodies, and this risk may be assumed to apply also to anti-CD37 antibodies. Subjects whose Screening labs show anti-hepatitis B core antibody (HBc antibody) positivity, but have negative HBV DNA by PCR are eligible to enroll on this study. Although some subjects who are HBc antibody positive with negative PCR may have had passive transfer of antibody from intravenous IgG, it cannot be known for certain that any such subject did not have natural HBV infection. Therefore, all subjects who are HBc antibody positive at screening should receive Hepatitis B prophylaxis with lamivudine, entecavir, or tenofovir per National Comprehensive Cancer Network (NCCN) infection guidelines. These subjects will also be monitored for potential HBV reactivation (manifest as detectable HBV DNA by quantitative PCR). Subjects will be tested monthly,

starting at Week 8, for the duration of BI 836826 therapy and every 3 months thereafter for 1 year from the last dose of BI 836826 during study participation. Following the completion of study participation, monitoring for HBV reactivation will be conducted per standard of care, at the discretion of the investigator. If there is evidence of HBV reactivation, immediately discontinue BI 836826 and idelalisib.

5.7.12. Further Safety Information

Further safety information regarding the study drug may be found in the idelalisib and BI 836826 IBs.

5.8. Prior and Concomitant Medications

5.8.1. Idelalisib

Subjects must receive trimethoprim-sulfamethoxazole or other established prophylaxis for PJP throughout the course of idelalisib treatment. Prophylaxis will continue for a minimum period of 2-6 months after idelalisib discontinuation and until the CD4+ T-cell count is documented to be >200 cells/mcL. The duration of prophylaxis should be based on clinical judgment and may take into account risk factors such as concomitant corticosteroid treatment and prolonged neutropenia after idelalisib treatment ends.

5.8.2. BI 836826

5.8.2.1. Infusion-Related Reactions

Infusion-Related Reactions are related to cytokine-release resulting from the interaction of antibody with antigen on circulating hematopoietic cells, with increasing risk at higher infusion dose rates or increments. Pre-medication is mandatory 30-120 minutes prior to the administration of BI 836826 to mitigate the risk for IRR, see [Table 5-4](#). In case a contra-indication for 1 of the drug exists, the drug may be replaced or omitted.

If BI 836826 has been well tolerated without signs of IRRs during the sixth or a later administration (ie, in Week 8 or later), the glucocorticoid dose may be stepwise reduced during subsequent infusions while the other drugs are maintained. If BI 836826 is tolerated without IRR after pre-medication according to [Table 5-4](#) Level -2, the investigator may individually decide whether to administer pre-medication for subsequent treatments and which of the recommended drugs to use.

If IRRs are observed at infusions with reduced pre-medication, the pre-medication triplet at doses as outlined for the first 4 infusions should continue to be used for all administrations.

Table 5-4. Premedication for BI 836826

Week	Subjects Requiring Premedication	Premedication	Completion Prior to BI 836826
2-8	all subjects	Analgesic/Antipyretic PO or IV ¹ Antihistamine PO or IV ² Glucocorticoid IV, equivalent to prednisolone 100 mg	60-120 minutes
10-46	all subjects with IRR in the previous infusion or with ALC \geq 25000/ μ L	Analgesic/Antipyretic PO or IV ¹ Antihistamine PO or IV ² Glucocorticoid IV, equivalent to prednisolone 100 mg	60-120 minutes
10-46	subjects without IRR in previous infusion and ALC < 25000/ μ L	Premedication Level -1: Analgesic/Antipyretic PO or IV ¹ Antihistamine PO or IV ² Glucocorticoid IV, equivalent to prednisolone 50 mg	30-120 minutes
10-46	subjects with ALC < 25000/ μ L and without IRR and premedication at level -1 at previous infusion	Premedication Level -2: Analgesic/Antipyretic PO or IV ¹ Antihistamine PO or IV ² Glucocorticoid IV, equivalent to prednisolone 25 mg	30-120 minutes
12-46	subjects with ALC < 25000/ μ L and without IRR and premedication at level -2 at previous infusion	Premedication at the discretion of the investigator	

1. equivalent to Acetaminophen/Paracetamol 1000 mg
2. equivalent to diphenhydramine 50 mg IV

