5.4. Dosage and Administration

This study has been terminated, with 2 subjects enrolled in the Phase 1b portion of the study. The 2 subjects enrolled may remain on study at the current dose levels for both treatments.

Dosing (Phase 1b and Phase 2):

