BI 836826 Administration ⁷		X		X	X	X	X	X	X	
Adverse Events		X		X	X	X	X	X	X	X
Concomitant Medication		X		X	X	X	X	X	X	X

1 Chemistry & hematology will be obtained a minimum of 3 times in the first week following completion of the first 50% dose of BI 836826 on Day 9; and once after the first full dose of BI 836826 on Day 22, then a minimum of weekly x 6 weeks, then prior to each BI 836826 infusion. All subjects should have blood counts monitored at least every two weeks for the first 6 months of idelalisib treatment. For subjects who develop ANC 0.5 to < 1.0 Gi/L, blood counts should be monitored at least weekly

2 CMV surveillance for active disease must be conducted approximately every 4 weeks throughout the course of idelalisib treatment.

3 Samples for immune monitoring were drawn at Baseline prior to the first dose of idelalisib. With the implementation of Amendment 4, only CD4 will be collected at the time points specified.

- 4 With the implementation of Amendment 4, PK and biomarker samples are no longer being collected and subjects are past Week 16. Samples for BI 836826 anti-drug antibody testing will be drawn at the time points indicated. For additional information see [Appendix Table 2](#) PK and Anti-Drug Antibody Sampling and the Laboratory Manual.

■

- 6 Idelalisib is taken BID; on BI 836826 dose days the morning dose is taken in the clinic approximately 60 minutes prior to starting the BI 836826 infusion
- 7 BI 836826 given via IV infusion at the indicated time points, beginning with 10 mg and ramping up through 50% to 100% of the intended dose over 4 weeks
- 8 The 30-day Follow-up assessment will be done following last dose of BI 836826 (no later than Week 50).

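### Table 5-4 leaves out the lasting full-premedication rule that Protocol Section 5.8.2.1 sets after an infusion reaction on reduced premedication (minor inconsistency in a safety instruction)

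*Protocol*

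**What the plan says.** Protocol Section 5.8.2.1 first allows premedication to be reduced. If the sixth or a later infusion (Week 8 onward) passes without an IRR, "the glucocorticoid dose may be stepwise reduced during subsequent infusions while the other drugs are maintained". It then limits that permission: if an IRR is seen at an infusion given with reduced premedication, "the pre-medication triplet at doses as outlined for the first 4 infusions should continue to be used for all administrations".

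Table 5-4, in the same subsection, sorts subjects into rows. From Week 10 (Week 12 for the last row) these are:

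- Full triplet, 100 mg prednisolone-equivalent: "all subjects with IRR in the previous infusion", or a high ALC (25000/µL or more).
- Level -1, 50 mg: "subjects without IRR in previous infusion and ALC < 25000"/µL.
- Level -2, 25 mg: low ALC, "without IRR and premedication at level -1 at previous infusion".
- Investigator discretion: low ALC, "without IRR and premedication at level -2 at previous infusion".

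The table's two footnotes give only drug equivalents. Section 5.4.2.1 refers back to Section 5.8.2. Section 5.4.2 adds a premedication rule only for delays of more than 4 weeks.

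The instruction is still in use. Section 5.4 states: "The 2 subjects enrolled may remain on study at the current dose levels for both treatments". Footnote 4 to Appendix Table 1 says that "PK and biomarker samples are no longer being collected and subjects are past Week 16". Infusions are scheduled to Week 46.

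**The concern.** The sentence in the text looks at the subject's whole history: one reaction on reduced premedication and the full triplet should stay. The table looks back one infusion only. After a single clean infusion on the restored triplet, a low-ALC subject who has already reacted on a reduced dose meets the Level -1 row again, and two further clean infusions lead to discretion. The text sends the reader to the table, and nothing in the table points back to the exception.

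What is at stake is premedication in someone who has shown that they react when it is reduced. IRR was the most frequent adverse event in the CLL monotherapy trial of BI 836826 (25 of 36 subjects, 69%). Three of those subjects had Grade 3 reactions, two of which led to discontinuation (Section 1.3.3). These are not rates of late IRR on reduced premedication. The documents give no such rate.

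**Working it through.** The plan states no figure to reproduce, so the check traces the text and the table through the infusion schedule.

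**Schedule** (Section 5.4.2 and Appendix Table 1). Infusions fall in Weeks 2, 2, 3, 4, 6, 8, 10, 12, 14, 16, 18, 22, 26, 30, 34, 38, 42 and 46. That is 18, as the protocol states, and the sixth is Week 8. The first infusion that can be given with reduced premedication is therefore Week 10.

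**Two paths after one IRR on reduced premedication.** Assume ALC below 25000/µL, later infusions clean and on schedule, and the fastest step-down that the table permits.

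- Text: 100 mg at every later infusion.
- Table: 100 mg at the next infusion (IRR at the previous one), then 50 mg, then 25 mg, then discretion.

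**Shortfall of listed doses** (text minus table):

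- 3 or more infusions left: (100 − 100) + (100 − 50) + (100 − 25) = 0 + 50 + 75 = 125 mg
- 2 left: 0 + 50 = 50 mg
- 1 or none left: 0 mg

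**Discretionary infusions** = infusions left − 3, and not less than 0.

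| IRR at Week | Infusions left | Listed-dose shortfall (mg) | Discretionary infusions |
|---|---|---|---|
| 10 | 11 | 125 | 8 |
| 12 | 10 | 125 | 7 |
| 14 | 9 | 125 | 6 |
| 16 | 8 | 125 | 5 |
| 18 | 7 | 125 | 4 |
| 22 | 6 | 125 | 3 |
| 26 | 5 | 125 | 2 |
| 30 | 4 | 125 | 1 |
| 34 | 3 | 125 | 0 |
| 38 | 2 | 50 | 0 |
| 42 | 1 | 0 | 0 |
| 46 | 0 | 0 | 0 |

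Example: after an IRR at Week 18, both paths give 100 mg at Week 22. The table then permits 50 mg at Week 26, 25 mg at Week 30, and discretion at Weeks 34, 38, 42 and 46.

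**What is already past.** Both subjects are beyond Week 16, so a new IRR can arise only from Week 18. An IRR at Weeks 10 to 16 would still count, because the text rule is lasting, but part of the difference may be over. After an IRR at Week 10, for instance, the 50 mg and 25 mg steps fall at Weeks 14 and 16, which leaves only the 8 discretionary infusions from Week 18 to Week 46. The documents do not say whether either subject had such an IRR.

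**The case against.** The strongest reply is that the protocol already deals with this. The exception stands directly above Table 5-4, straight after the sentences that allow step-down, and Section 5.4.2.1 sends sites to Section 5.8.2 as a whole. Read together they give one workable instruction: the text sets the limit and the table lists the dose levels. Step-down is optional, so a site that never uses it sees no difference. On this view a short note to sites would do, and a protocol modification in a terminated study is out of proportion.

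Much of this stands. The text is best read as governing, and harm needs a site to use the table without the sentence above it. But a table row that lists a dose which the text advises against is more than a missing cross-reference, and the table is what the text tells sites to look at.

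A reader might also infer that the table permits something the text forbids. The wording does not go that far. The exception says that the triplet should be used, while the same subsection calls premedication before infusion mandatory. A reader might likewise infer that the table ignores the reaction altogether. It does not: the infusion right after an IRR gets the full triplet. Only the lasting part is lost.

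**Conclusion.** The inconsistency is real and minor. For Week 10 onward, Table 5-4 omits the lasting part of the Section 5.8.2.1 rule. On the table's fastest path the listed doses fall short by 125, 50 or 0 mg prednisolone-equivalent in total, depending on the infusions left. The number of discretionary infusions that follow runs from 8 (IRR at Week 10) through 5 (Week 16) and 4 (Week 18) to 0 (Week 34 or later). Any further difference at those infusions depends on what the investigator chooses. The sums assume one IRR on reduced premedication, no later IRR, infusions on schedule and ALC below 25000/µL throughout.

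At most the 2 continuing subjects are affected. A reader might infer that the safety results or the dose-finding are compromised, and the documents do not support that. Adverse events are only listed (SAP Section 7.1.6), dose-limiting toxicity will not be evaluated (SAP Section 7.6), and IRRs of any grade are in any case excepted from the dose-limiting toxicities (Protocol Section 5.5). Nor is the premedication design itself in question: the rule in the text is sound, and the table does not carry it.

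**What to change.** Bring Table 5-4 into line and leave the Section 5.8.2.1 text unchanged:

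- In the full-triplet row for Weeks 10-46, add: *or IRR at any earlier infusion given with reduced premedication*.
- In the Level -1, Level -2 and discretion rows, add: *and no IRR at any earlier infusion given with reduced premedication*.

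This wording also covers a subject whose IRR came before Week 18.

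The cost is one condition in four rows and documented IRB/IEC approval before use (Protocol Section 9.2.1). An affected subject would receive somewhat more corticosteroid than on the table's path: up to the listed-dose shortfall above, plus at most 100 mg at each infusion that would otherwise be discretionary. The text already calls for that dose. No visits or procedures are added.

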5.8.2.2. Tumor Lysis Syndrome

Subjects with a high tumor burden or preexisting renal dysfunction should receive prophylaxis for TLS prior to the initiation of treatment. These subjects must be well hydrated. It is desirable to maintain a fluid intake of approximately 3 liters per day for 1-2 days before the first 50% dose of BI 836826. Treatment with allopurinol (\geq 300 mg p.o./day) or a suitable alternative (eg, rasburicase) starting \geq 24 hours prior to the first infusion should be considered. Subjects should continue to receive repeated prophylaxis with allopurinol and adequate hydration prior to each subsequent infusion, if deemed appropriate by the investigator. Older and frail subjects will need special individualized care in fluid management, as 3 liters per day may not be tolerated. Rasburicase may be particularly indicated in such subjects. For all subjects, electrolytes should be monitored and corrected, fluid balance and renal function should be monitored, and supportive care should be administered, including dialysis as indicated.

5.8.2.3. Hepatitis B

All subjects who are HBc antibody positive at screening should receive Hepatitis B prophylaxis. Refer to Section 5.7.11 for specific treatment recommendations.

5.8.3. Anticancer or Experimental Therapies Other than Idelalisib or BI 836826

No other anticancer therapies (including systemic chemotherapy, radiation, antibody therapy, immunotherapy, or other experimental therapies) of any kind are permitted while the subject is participating in the study. Subjects are not allowed to participate concurrently in any other therapeutic clinical study.

5.8.4. Granulocyte Colony-Stimulating Factors and Erythropoietin

Granulocyte-macrophage colony-stimulating factors (GM-CSF) should not be administered given the potential for GM-CSF-related inflammatory symptoms. The use of supportive care agents such as Granulocyte colony-stimulating factor (G-CSF) agents or erythropoietic agents are permitted in compliance with regional prescribing information.

